7.4.2. Ocular Symptoms of AR

The ocular symptom endpoints for efficacy will be calculated from the daily subject-rated ocular symptom scores. The three individual ocular symptoms that each subject will assess throughout the study are:

- Eye Itching and Burning
- Eye Watering
- Eye Redness

The total ocular symptom score (TOSS) is a composite score of the above three components with a maximum score of 9.

Rating

Subjects will use the following scale to assess the severity of each of the three symptoms above:

Similar to the nasal symptom assessments, the subjects will be instructed to score and document their ocular symptoms in the diary in a reflective manner (rTOSS) TWICE daily at the same time as assessing their reflective nasal symptoms.

Table 4 Table scoring of ocular symptoms

severity (score) /symptom	None (0)	Mild (1)	Moderate (2)	Severe (3)
Eye itching/ Burning	Symptom is not present	sign/symptom is clearly present but minimal awareness; easily tolerated	definite awareness of sign/symptom that is bothersome but tolerable	sign/symptom is hard to tolerate; causes interference with activities of daily living and/or sleeping
Tearing/watering				
Eye redness				

7.4.3. Anterior rhinoscopy findings of AR

The anterior rhinoscopy change will be calculated from the subject nasal concha mucosa symptoms score. The 4 individual score that each subject will assess throughout the study are:

- swelling of inferior nasal concha mucosa
- color of inferior nasal concha mucosa
- watery secretion volume
- description of rhinorrhea

Rating

Investigator will use the following scale to assess the severity of each of the three symptoms above:

The investigator used the following 0 to 3 scale to assess the severity of each item at baseline (Visit 2) and every visit of study (Visits 3, 4, 5/Early Withdrawal).

Table 5 Table scoring of anterior rhinoscopy findings

Items	None (0)	Mild (1)	Moderate (2)	Severe (3)
Swelling of inferior nasal concha	None	To center turbinate	Between 1 and 3	Cannot observe center turbinate

Items	None (0)	Mild (1)	Moderate (2)	Severe (3)
Color of inferior nasal concha mucosa	Normal	Light red	red	pale
Watery secretion volume	None	Adhesion level	Between 1 and 3	Fullness
Description of rhinorrhea	None	purulent	Viscous	Aqueous

7.4.4. Overall evaluation of Response to therapy by investigator

The investigator will evaluate subject's overall response to therapy (improvement in the symptoms of AR) compared with Visit 2, in accordance with the Time and Event Table, using 7 point categorical scale below and record it in the CRF.

1. Significantly Improved
2. Moderately Improved
3. Mildly Improved
4. No Change
5. Mildly worse
6. Moderately worse
7. Significantly worse

7.4.5. Primary Efficacy Endpoints

The primary efficacy endpoint will be the mean change from baseline over the first 2 weeks treatment period in daily reflective total nasal symptom scores (rTNSS) in subjects ages 2 to 12 years.

7.4.6. Secondary Efficacy Endpoints

The secondary endpoints for the study will consist of the following measures:

- Overall evaluation of response to therapy (evaluated on a 7-point categorical scale) after the first 2 weeks treatment (day 15)
- The mean change from baseline of study intranasal finding score by anterior rhinoscopy at the first 2 weeks treatment (day 15)

- Mean change from baseline over the first 2 weeks treatment period in the daily, reflective total ocular symptoms score (rTOSS)
- Rescue loratadine use (mean rescue-free days) over the first 2 weeks treatment period
- Mean change from baseline over the 4 weeks treatment period in daily rTNSS
- Overall evaluation of response to therapy after 4 weeks treatment period (day 29)
- The mean change from baseline of intranasal finding score by anterior rhinoscopy at the end of treatment (day 29)
- Mean change from baseline over the 4 weeks treatment period in the daily rTOSS
- Rescue loratadine use (mean rescue-free days) over the entire 4 weeks

7.5. Safety

Planned time points for all safety assessments are listed in the Time and Events Table (Section 7.1). Additional time points for safety tests (including but not limited to vital signs, physical exams and laboratory safety tests) may be added during the course of the study based on newly available data to ensure appropriate safety monitoring.

The safety endpoints for the study will consist of the following assessments. More detailed information is provided in Study Assessments and Procedures (Section 7.1)

- Frequency and type of clinical adverse events
- Results of clinical laboratory test (hematology and chemistry)
- Results of physical and nasal examinations
- Vital signs (temperature, systolic and diastolic blood pressures, pulse rate, respiratory rate)

7.5.1. Adverse Events (AE) and Serious Adverse Events (SAEs)

The definitions of an AE or SAE can be found in [Appendix 3](#).

7.5.1.1. Time period and Frequency for collecting AE and SAE information

- The investigator or site staff is responsible for detecting, documenting and reporting events that meet the definition of an AE or SAE.
- Serious AEs will be recorded from the time the consent form is signed until the follow-up contact. All AEs will be recorded from the start of study treatment until the follow-up contact.
- All SAEs will be recorded and reported to GSK within 24 hours, as indicated in [Appendix 3](#). Investigators will assess causality and tick the box on SAE Form in eCRF within 72 hours. If not completed in 72 hours, protocol deviation will be entered.

- Investigators are not obligated to actively seek AEs or SAEs in former study subjects. However, if the investigator learns of any SAE, including a death, at any time after a subject has been discharged from the study, and he/she considers the event reasonably related to the study treatment or study participation, the investigator must promptly notify GSK.

NOTE: The method of recording, evaluating and assessing causality of AEs and SAEs plus procedures for completing and transmitting SAE reports to GSK are provided in [Appendix 3](#)

7.5.1.2. Method of Detecting AEs and SAEs

Care will be taken not to introduce bias when detecting AEs and/or SAEs. Open-ended and non-leading verbal questioning of the subject is the preferred method to inquire about AE occurrence. Appropriate questions include:

- “How are you feeling?” **or** “How does your child seem to feel?”
- “Have you had any (other) medical problems since your last visit/contact?” **or** “Has your child had any (other) medical problems or seem to act differently in any way since his/her last visit/contact?”
- “Have you taken any new medicines, other than those provided in this study, since your last visit/contact?” **or** “Has your child needed to take any medicines, other than those provided in this study, since his/her last visit/contact?”

7.5.1.3. Follow-up of AEs and SAEs

After the initial AE/SAE report, the investigator is required to proactively follow each subject at subsequent visits/contacts. All SAEs, and non-serious AEs of special interest (as defined in Section 4.5.1) will be followed until resolution, until the condition stabilizes, until the event is otherwise explained, or until the subject is lost to follow-up. Further information on follow-up procedures is given in [Appendix 3](#).

7.5.1.4. Regulatory Reporting Requirements for SAEs/ ADRs

SAEs shall be reported to CFDA as required per regulation of *Provision for Drug Registration and Good Clinical Practice of Pharmaceutical Products*, ADRS shall be reported to Adverse Drug Monitoring Center as required by regulation of *Provision for Adverse Drug Reaction Reporting and Monitoring (Order 81. Of the Ministry of Health)*.

Prompt notification by the investigator to GSK of SAEs is essential so that legal obligations and ethical responsibilities towards the safety of subjects and the safety of a product under clinical investigation are met.

GSK has a legal responsibility to notify both the local regulatory authority and other regulatory agencies about the safety of a product under clinical investigation. GSK will comply with country specific regulatory requirements relating to safety reporting to the regulatory authority, Institutional Review Board (IRB)/Independent Ethics Committee (IEC) and investigators.

Investigator safety reports are prepared for suspected unexpected serious adverse reactions according to local regulatory requirements and GSK policy and are forwarded to investigators as necessary.

An investigator who receives an investigator safety report describing a SAE(s) or other specific safety information (e.g., summary or listing of SAEs) from GSK will file it with the IB and will notify the IRB/IEC, if appropriate according to local requirements.

7.5.2. Physical Exams

- A complete physical examination will include, at a minimum, assessment of the Cardiovascular, Respiratory, Gastrointestinal and Neurological systems. Height and weight will also be measured and recorded.
- Investigators should pay special attention to clinical signs related to previous serious illnesses
- Physical examination results will be documented in the source documents only.

7.5.3. Nasal Exams

A detailed nasal examination of the mucosa, septum, secretions, nasal patency, size of any polyps and ulcers will be performed by the investigator at all visits (Visits 1 – 5 or Early Withdrawal) and the findings recorded on the nasal examination CRF page. Any unfavorable changes that are not reflective of the symptoms of AR from the Visit 1 assessment will be recorded as an adverse event, documenting the start and stop dates of the adverse event. A diagnosis of nasal candidacies should be reported as an adverse event.

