4. STUDY DESIGN

4.1. Overall Design

Protocol waivers or exemptions are not allowed with the exception of immediate safety concerns. Therefore, adherence to the study design requirements, including those specified in the Time and Events Table (Table 2), Section 7.1, are essential and required for study conduct.

- This phase IV study will be a randomized, double-blind, placebo-controlled, multicenter parallel study.
- Eligible subjects will participate in the study which begins with a 4 to 14-day run-in period with no treatment (Visit 1).
- After a minimum 4-day run-in period, subjects meeting the randomisation criteria will be randomised in a 1:1:1 ratio to the following three treatment arms (Visit 2);, in accordance with a computer generated randomization schedule provided by GlaxoSmithKline (GSK), via an Interactive Voice Response System (IVRS) called Registration and Medication Ordering System (RAMOS).
 - FFNS 110 µg once daily
 - FFNS 55 µg once daily
 - Vehicle placebo aqueous nasal spray
- The randomization will be centralized and stratified by age (≥ 2 to ≤ 6 years and > 6 to ≤ 12 years) and by classification of AR (intermittent vs. persistent) to ensure treatment balance in age groups and AR classification groups for both safety and efficacy assessments. Subjects with 6 years old and less than 7 years old will be treated as 6 years of age; these subjects will be analysis in group of 2 to 6 years. Subjects with 12 years old and less than 13 years old will be treated as 12 years of age and will be analysis in group of 6 to 12 years.
- Following the 28-day treatment period, subjects will be followed up by telephone contact within 5 ± 2 days after the last dose. The following procedures will be performed: Adverse Event (AE)/ Serious Adverse Event (SAE) assessment. Subjects will be discharged from the study upon completion of the follow-up phone call.

In summary, this study is comprised of screen, run-in period (4 to 14 days), double-blind treatment period (28 days) and follows up period (3 to 7 days). Subjects entering the study will participate for maximum of 50 days, including five clinical visits and a follow-up telephone contact.

Figure 1 Study Design

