7.3. Screening and Critical Baseline Assessments

All demographic and baseline assessments will be completed according to the Time and Events schedule in Section 7.1. Safety parameters physical exams, vital signs, electrocardiogram (ECG) and clinical safety laboratory assessments will be defined as baseline at Visit 1. Nasal exams baseline will be assessed at Visit 2.

Medical/medication history will be assessed as related to the eligibility criteria listed in Section 5. Height, weight, medical conditions will also be assessed at baseline. SAE information (see Section 12.3.2), if applicable, will also be assessed at baseline.

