9.4.3. Other Analyses

Safety analysis

Safety data will be summarized and/or listed by treatment group for the ITT population.

Extent of Exposure

The extent of exposure to study drug will be summarized by treatment group.

Adverse Events (AEs)

AEs will be coded using the standard GSK dictionary, MedDRA, and grouped by body system. AEs occurring pre-treatment, during active treatment and post-treatment will be summarized separately. The number and percentage of subjects experiencing at least one AE of any type, AEs within each body system and AEs within each preferred term will be presented for each treatment group. Separate summaries will be provided for all AEs, drug related AEs, SAEs, and for AEs leading to withdrawal.

Clinical Laboratory Evaluations

Clinical laboratory evaluations, including hematological and clinical chemistry, will be summarized by treatment group for each visit. Further details will be provided in the RAP.

Nasal Examinations

Nasal examinations will be performed at each visit, and will include assessments of nostril patent, septum, mucosa, secretions, ulcers, and polyposis. Nasal examination results will be summarized by visit for each of the 6 examination parameters listed above. At all visits, frequencies of classifications (yes/no, absent/present) will be calculated. Shift from baseline (Visit 2) will be summarized for each individual nasal examination parameter. Abnormal nasal examination results will be listed.

Vital Signs Assessments

Vital signs will be summarized for each clinic visit. Further details will be provided in the RAP.

Deaths and SAEs

All SAEs will be tabulated and listed by treatment group. Deaths and SAEs will be documented in case narrative format.

10. STUDY GOVERNANCE CONSIDERATIONS**10.1. Posting of Information on Publicly Available Clinical Trial Registers**

Study information from this protocol will be posted on publicly available clinical trial registers before enrollment of subjects begins.

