11.4.2.2. Treatment States for AE Data

Treatment State	Definition
Pre-Treatment	AE Start Date < Study Treatment Start Date
On-Treatment	Study Treatment Start Date ≤ AE Start Date ≤ Study Treatment Stop + 1
Post-Treatment	AE Start Date > Study Treatment Stop Date + 1
Onset Time Since 1 st Dose (Days)	If Treatment Start Date > AE Onset Date = AE Onset Date - Treatment Start Date; If Treatment Start Date ≤ AE Onset Date = AE Onset Date - Treatment Start Date + 1 Missing otherwise.

Treatment State	Definition
Duration (Days)	AE Resolution Date - AE Onset Date + 1
Drug-related	If relationship is marked 'YES' on Inform/CRF OR value is missing.

NOTES:

- If the AE onset date is missing or partial then the AE will be considered on-treatment unless there is evidence to the contrary (e.g. the month of the onset date is present and is less than the month of the first dose of study treatment).
- AEs reported by subjects who did not receive treatment will be considered pre-treatment.
- Any SAEs for screen failures, run-in failures or subjects who were randomised but did not receive treatment will be classified as pre-treatment SAEs.

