- The baseline value for a nasal examination endpoint will be the most recent recorded value for that endpoint before dosing on Day 1.
- Nasal examinations will be collected during Visits 1-5 or Early Withdrawal. Summary statistics for mucosa, septum, secretions, nasal patency, size of any polyps and ulcers will be provided at Visit 1-5 or Early Withdrawal.
- A summary of change from baseline in nasal examinations at endpoint (Vsit5/Early Withdrawal) will be made.

Vital Signs

- The baseline value for a vital sign endpoint will be the most recent recorded value for that endpoint before dosing on Day 1.
- Vital signs will be collected during Visit 1 (Screening) and Visit 5 (Week 4)/Early Withdrawal. Summary statistics for systolic blood pressure (mmHg), diastolic blood pressure (mmHg), heart rate (beats/min), temperature (°C), and respiratory rate (breaths/min) will be provided at baseline and Visit 5 or Early Withdrawal.
- A summary of change from baseline in vital signs at endpoint (Vsit5/Early Withdrawal) will be made.

12-Lead ECG

- The baseline value for an ECG endpoint will be the most recent recorded value for that endpoint before dosing on Day 1.
- Twelve-lead ECGs will be performed at Visit 1 (Screening) and Visit 5 (Week 4)/Early Withdrawal. ECG results of "normal", "abnormal, not clinically significant (NCS)", and "abnormal, clinically significant (CS)" will be summarized at baseline and Visit 5 or Early Withdrawal.
- A listing of subjects with abnormal clinically significant ECG evaluations and/or clinically significant change(s) in ECG evaluations will be provided.

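### Nasal-examination adverse events are judged against Visit 1 while the nasal baseline is Visit 2, so some untreated run-in findings can be counted as on-treatment events

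*Protocol*

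**What the plan says.** Protocol 7.5.3 calls for a nasal examination at every clinic visit and sets its own trigger for an adverse event: "Any unfavorable changes that are not reflective of the symptoms of AR from the Visit 1 assessment will be recorded as an adverse event". The same sentence asks for start and stop dates.

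The other sections use a later reference:

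- Protocol 7.3: "Nasal exams baseline will be assessed at Visit 2".
- Protocol 9.4.3: "Shift from baseline (Visit 2) will be summarized for each individual nasal examination parameter".
- SAP 11.6.3: "The baseline value for a nasal examination endpoint will be the most recent recorded value for that endpoint before dosing on Day 1". With the schedule in Protocol 7.1 this is normally the Visit 2 examination.

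On the recording window, Protocol 7.5.1.1 states: "All AEs will be recorded from the start of study treatment until the follow-up contact". Footnote 6 of the Time and Events Table says the same. Only serious events are collected from consent.

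SAP 11.4.2.2 assigns events to phases by date alone. An event is pre-treatment if "AE Start Date < Study Treatment Start Date" and on-treatment if "Study Treatment Start Date ≤ AE Start Date ≤ Study Treatment Stop + 1". A missing or partial onset date defaults to on-treatment unless there is evidence to the contrary.

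**The concern.** Visit 1 and Visit 2 are 4 to 14 days apart, and no study drug is given between them (Protocol 4.1). The examiner is therefore given one reference visit for deciding whether a nasal change is an adverse event, and the analyst another for deciding whether it is a change from baseline. The reference in 7.5.3 also conflicts with the protocol's own AE window. A non-AR finding seen at Visit 2 before dosing is a change from Visit 1, and so an event by 7.5.3, but it precedes the start of non-serious AE recording in 7.5.1.1.

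Safety is the secondary objective and the nasal examination is one of its endpoints. The risk table in Protocol 4.5.1 names nasal events and relies on focused nasal examinations as mitigation. What is at stake is whether nasal events reported as on-treatment began after the first dose, and whether a finding that was clear at baseline and reappears on drug is captured as an event.

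**Working it through.** The plan states no figure on this point, so the check is one of logic, in three steps.

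**1. Do the two references give different answers?** Take a nasal finding that is not reflective of AR as absent (0) or present (1) at Visit 1, Visit 2 (before dosing) and an on-treatment examination such as Visit 3. Judge the on-treatment examination by each rule.

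| Visit 1 | Visit 2 | Visit 3 | Unfavourable change from Visit 1 (7.5.3) | Shift from Visit 2 (7.3, 9.4.3) |
|---|---|---|---|---|
| 0 | 0 | 0 | no | no |
| 0 | 0 | 1 | yes | yes |
| 0 | 1 | 0 | no | no |
| 0 | 1 | 1 | **yes** | **no** |
| 1 | 0 | 0 | no | no |
| 1 | 0 | 1 | **no** | **yes** |
| 1 | 1 | 0 | no | no |
| 1 | 1 | 1 | no | no |

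The rules disagree in 2 of 8 patterns. In the first (0, 1, 1) the finding began before any drug but meets the 7.5.3 trigger. In the second (1, 0, 1) the finding is new relative to baseline but does not meet it. In the 0, 1, 0 pattern the Visit 2 examination is itself a change from Visit 1, so the dating question in step 2 applies there too.

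**2. Where does a run-in finding land in the AE tables?** Apply the date rule of SAP 11.4.2.2, with treatment starting on the Visit 2 date.

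| Onset as entered | SAP class |
|---|---|
| A day in the run-in | Pre-treatment |
| The Visit 2 date, even if seen before the dose | On-treatment |
| Missing, or partial without contrary evidence | On-treatment |
| The Visit 3 date | On-treatment |

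Visit 2 is the first scheduled examination after Visit 1 (Protocol 7.1), so for a finding without symptoms the Visit 2 date is a plausible entry. The first dose is given in clinic that same day (Protocol 6.2), and the date rule cannot separate before from after. The protocol does not state that the Visit 2 nasal examination precedes the dose.

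**3. How large could it be?** The documents give no incidence of new nasal findings in the run-in. Assume 1% to 5%:

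- All randomised: 360 × 0.01 = 3.6 to 360 × 0.05 = 18 children.
- Per arm: 120 × 0.01 = 1.2 to 120 × 0.05 = 6 children.

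These are counts of children with such a finding. They are a ceiling on the added on-treatment events, since correctly dated findings are classed as pre-treatment.

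**The case against.** The strongest reply is that the plan already contains safeguards. Non-serious AE recording starts at first dose, so a run-in finding that resolves before dosing falls outside the window. 7.5.3 asks for a start date, and a correctly dated run-in onset is pre-treatment under the SAP. Protocol 9.4.3 says pre-treatment events are summarised separately. Eligibility is rechecked at Visit 2, which removes some nasal conditions altogether. All of this stands and narrows the point to findings dated on or after the Visit 2 date, or with a missing or partial date. It does not remove it: the start-date safeguard depends on an onset that the examiner may not know, and the SAP's list of safety tables has all-AE summaries only for the treatment and post-treatment periods.

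A reader might infer three stronger things that the documents do not support.

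- *That run-in findings in general become adverse events.* The AE window and the date rule exclude those that resolve before dosing and class correctly dated ones as pre-treatment.
- *That a finding which clears by Visit 2 and returns is lost.* It is still entered on the nasal examination CRF page and summarised by visit. The general AE definition in Protocol 12.3.1 may also capture it. Only the 7.5.3 trigger misses it.
- *That the drug-placebo contrast is materially diluted.* Assume true nasal-AE rates p of 10% and 5%, and a run-in rate r of 2%, 5% or 10%, with every run-in finding counted on treatment. The observed rate 1 − (1 − p)(1 − r) then gives 11.8% vs 6.9%, 14.5% vs 9.75%, and 19.0% vs 14.5%. The ratio falls from 2.0 to 1.71, 1.49 and 1.31. None of these rates is in the documents, and the calculation is an upper bound. The plan reports counts and percentages, with no modelling of safety and no risk ratio. On the same inputs the risk difference moves only from 5.0 to 4.9, 4.75 and 4.5 points.

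Nor would disagreement between AE and shift tables prove a fault. The SAP's shifts run from baseline to Visit 5 or early withdrawal, while AE tables cover the whole treatment period and leave out AR-reflective changes, so they would differ even with a common reference.

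**Conclusion.** The contradiction is real and in current text: 7.5.3 refers to Visit 1, while 7.3, 9.4.3 and SAP 11.6.3 refer to Visit 2 or the last pre-dose value, and 7.5.1.1 starts non-serious AE recording at first dose. Its effect is small. Some run-in findings can be counted as on-treatment through the way they are dated, and some returning findings do not meet the nasal AE trigger.

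The added events would slightly raise absolute nasal-AE rates. They are equal in expectation across arms, because their onset precedes randomisation and dating is done blind. For returning findings, the children at risk are likewise balanced by randomisation, but whether a finding returns is settled on treatment, so equality there is an assumption. The size rests on the assumed run-in incidence of 1% to 5%. The primary endpoint is not affected.

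**What to change.** In Protocol 7.5.3, replace the reference to the Visit 1 assessment with the pre-dose Visit 2 (baseline) assessment. Add that non-AR findings first seen at the pre-dose Visit 2 examination are baseline findings and not on-treatment adverse events, and that this examination is done before the first dose. Add a matching line to SAP 11.4.2.2, because its date rule would otherwise class anything dated on the Visit 2 day as on-treatment. Protocol 7.3, 7.5.1.1, 7.5.3 and 9.4.3 and SAP 11.4.2.2 and 11.6.3 would then agree.

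The cost is one phrase and one or two sentences in the protocol, a line in the SAP and a CRF instruction. The nasal examination is already scheduled at Visit 2, so no procedure is added. The change concerns how a finding is measured and classed, not how a child is treated.
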